#### **Exploratory Objectives**

To identify prognostic markers indicating the need for early intervention with Favipiravir in patients with COVID-19 infection.

To assess the pharmacokinetics and pharmacodynamics of Favipiravir

- Change in viral PCR titres at post-randomisation time points relative to baseline
- Change in host transcriptome profiles at post randomisation time points relative to baseline
- Computer tomography quantitative analysis
- Favipiravir pharmacokinetics and pharmacodynamics properties at day 5 to 10.

#### 7. TRIAL DESIGN

The study is an open-label, two arm, multi-centre randomised controlled clinical trial, to investigate the clinical effectiveness, safety, and resource utilisation of early treatment intervention in patients admitted to hospital with a suspected or proven COVID-19 infection. Subjects will be randomised 1:1 to one of two arms to receive:

- Arm 1: Favipiravir + standard of care
- Arm 2: Standard of care

The study treatment duration will be 10 days for each participant. If a participant recovers sufficiently to be discharged home before day 10, favipiravir will be supplied and the regimen completed as an outpatient.

Samples will be collected at three timepoints: baseline, between days 5 to 10 and days 14 to 28 (see section 9.4). In such instances where participants recover sufficiently to be discharged home and are not in hospital at the latter sample collection timepoints, they will be invited to return to facilitate this (provided that they are well enough and maximally twice).

For further information on activities at visits and schedule see Section 8.

Participants will exit the study at day 28 or if they become deceased.

#### 7.1. Data Cohort

In order to collect data on a representative sample of the full cohort of participants that could be entered into the study, a data cohort will be included in the study for the patients presenting in UK.

Data will be collected for participants with a diagnosis date within a window agreed by the lead sponsor and UK sites, in order to collect a large enough dataset for conclusions to be drawn. No personal identifiable data will be shared outside the care team, so no consent is required for this activity.

The following data will be collected:

All available baseline demographic and clinical data through to 28 days will be collected including clinical, physiological and blood results. Radiological analysis will be collected and included where available. Outcomes will be recorded.

#### 7.2. Trial Schematic

[figure not shown]

Figure 1TRIAL SCHEMATIC

#### 8. PARTICIPANT IDENTIFICATION, RECRUITMENT & ALLOCATION OF INTERVENTION

### 8.1. Study Participants

All patients requiring hospitalisation with suspected or confirmed COVID-19 (by SARS-CoV-2 or other National standard), fulfilling all the inclusion criteria and none of exclusion criteria, as defined below, will be considered for participation in this trial.

Globally, five hundred (500) participants will be recruited and randomised into one of two treatment arms in a 1:1 ratio.

#### Data cohort

Any suspected or proven Covid-19 patient admitted to hospital during a period agreed between the site and lead sponsor is to be included.

#### 8.2. Inclusion Criteria

The participant may enter the study if the following apply:

- 1. Adult participants: Signed informed consent or documented and witnessed oral informed consent
- 2. New admission to hospital for period expected to last  $\geq 1$  night
- 3. Suspected or confirmed COVID-19 infection

Patients are suspected of COVID-19 infection if they have the following:

Influenza like illness (fever ≥37.8°C or patient reported history of fevers and at least one of
the following respiratory symptoms, which must be of acute onset: persistent cough,
hoarseness, nasal discharge or congestion, shortness of breath, sore throat, wheezing or
sneezing).

#### And

• Finding from either a chest x-ray or CT suggestive of Covid-19 infection

#### And

- Alternative causes are considered unlikely
- 4. For women to be eligible to enter and participate in the study they should be of non-child-bearing and:
  - potential defined as either post-menopausal (12 months of spontaneous amenorrhea and ≥
     45 years of age) or physically incapable of becoming pregnant with documented tubal ligation, hysterectomy or bilateral oophorectomy or,
  - or of child-bearing potential have a negative pregnancy test at screening and agrees to remain sexually abstinent or use a method of contraception with a failure rate of < 1% per year as indicated in Appendix B during the treatment and for a period of 7 days after the last dose. Hormonal contraceptive methods must be supplemented by a barrier method.
- 5. Men who are sexually active must use an adequate method of contraception as listed in Appendix B, for a period of at least 7 days after the last dose

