#### 21. APPENDIX B: CONTRACEPTION

## 21.1 Women of Childbearing Potential (WOCBP)

A woman is fertile following menarche and until she becomes postmenopausal unless permanently sterile as per the below:

- Premenarchal female
- Postmenopausal female
- Premenopausal female with 1 of the following:
  - Documented hysterectomy
  - Documented bilateral salpingectomy
  - Documented bilateral oophorectomy

For women with permanent infertility of a medical cause other than the above, the investigator should determine study entry requirements.

Where fertility status is unclear additional evaluation should be considered.

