#### **Female Participants**

Female participants of childbearing potential are eligible to participate if they agree to one of the following forms of contraception that has a failure rate of < 1% per year:

- Combined (oestrogen- and progestogen- containing) hormonal contraception
  - Oral
  - Intravaginal
  - Transdermal
  - Injectable
- Progestogen only hormonal contraception
  - Oral
  - Injectable
- Progestogen- only contraceptive implant
- Intrauterine hormone-releasing system
- Intrauterine device
- Bilateral tubal occlusion
- Vasectomized partner
- Sexual abstinence

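### Inclusion criterion 4 spares premenopausal women with tubal ligation the screening pregnancy test, although Appendix B does not count tubal ligation as permanent sterility (minor safety correction)

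*Protocol*

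**What the plan says.** Section 8.1 makes eligibility depend on the listed criteria: patients "fulfilling all the inclusion criteria and none of exclusion criteria, as defined below, will be considered for participation in this trial". Criterion 4 in Section 8.2 then gives women two routes into the trial.

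- **First route, not of child-bearing potential.** The woman is post-menopausal or "physically incapable of becoming pregnant with documented tubal ligation, hysterectomy or bilateral oophorectomy or". No pregnancy test is attached to this route.
- **Second route, of child-bearing potential.** The text reads "or of child-bearing potential have a negative pregnancy test at screening", and she must also abstain or "use a method of contraception with a failure rate of < 1% per year as indicated in Appendix B".

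The synopsis lists the same procedures for the first route.

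Appendix B, Section 21.1, sets out its own rule: "A woman is fertile following menarche and until she becomes postmenopausal unless permanently sterile as per the below". For premenopausal women the list that follows has three entries: hysterectomy, "Documented bilateral salpingectomy" and bilateral oophorectomy. Tubal ligation is not among them. Section 21.2 asks female participants of childbearing potential to agree to "one of the following forms of contraception that has a failure rate of < 1% per year", and bilateral tubal occlusion is one of the methods it names.

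**The concern.** The two parts of the protocol classify the same woman differently. Under Appendix B a premenopausal woman with tubal ligation can still conceive and is using contraception. Under criterion 4 she cannot become pregnant, and so she is not tested.

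Exclusion 1 in Section 8.3 bars pregnancy on grounds of possible teratogenicity. The screening test is the protocol's stated means of finding a pregnancy that nobody has recognised before favipiravir starts at 1800 mg twice daily. What is at stake is therefore narrow: a missed unrecognised pregnancy in a woman given the drug. Contraception is adequate on either definition, and a known pregnancy is excluded in any case.

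**Working it through.** **Comparing the texts**

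| Procedure in a premenopausal woman | Criterion 4 (Section 8.2 and synopsis) | Appendix B |
|---|---|---|
| Hysterectomy | not of child-bearing potential | permanently sterile |
| Bilateral oophorectomy | not of child-bearing potential | permanently sterile |
| Bilateral salpingectomy | not listed | permanently sterile |
| Tubal ligation or occlusion | not of child-bearing potential | contraceptive method for women of childbearing potential |

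The lists differ in both directions. The last row matters for safety: criterion 4's first route exempts the woman, while Appendix B's definition would put her in the second route, where the test is required.

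**Does anything else require the test?**

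- Criterion 4 cites Appendix B only for contraceptive methods, so a site following Section 8.2 has no reason to apply the Section 21.1 definition to testing.
- The pre-randomisation tests in Section 9.4 are blood count, liver function, and urea and electrolytes. The baseline list in Section 10.1 contains no pregnancy test.
- Exclusion 1 in Section 8.3 names no test. The synopsis version adds one only where appropriate, and a site could fairly judge it inappropriate for a woman whom criterion 4 calls incapable of pregnancy.
- Clinician assessment of eligibility (Section 8.4) applies the same criterion 4.
- Section 21.1 adds "Where fertility status is unclear additional evaluation should be considered", but criterion 4 presents her status as settled.

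Several of these make a miss less likely. None requires the test.

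**Size of the gap**

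Inputs from the protocol: 500 participants randomised 1:1, hence 250 per arm; contraceptive failure below 1% per year for the listed methods (Section 21.2), taken here as 1%. Input not in the protocol: the share *p* of participants who are premenopausal women with tubal ligation, assumed to be 0.5% to 3%.

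Women affected = N × *p*. Upper bound on pregnancies = N × *p* × 0.01, which counts a full year of failures.

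| | *p* = 0.5% | *p* = 3% |
|---|---|---|
| Women, whole trial | 500 × 0.005 = 2.5 | 500 × 0.03 = 15 |
| Women, favipiravir arm | 250 × 0.005 = 1.25 | 250 × 0.03 = 7.5 |
| Pregnancies, favipiravir arm | 1.25 × 0.01 = 0.0125 | 7.5 × 0.01 = 0.075 |
| Pregnancies, both arms | 2.5 × 0.01 = 0.025 | 15 × 0.01 = 0.15 |

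For any other share, each 1% of participants means 5 women, 2.5 of them on favipiravir, and at most 0.025 pregnancies in that arm.

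**The case against.** The strongest reply is that sites face no conflict in practice. Criterion 4 is the operative rule, Appendix B concerns contraception and contains no testing requirement, and the synopsis and Section 8.2 agree in exempting tubal ligation. On this view only a mismatch of definitions remains. It is true that sites have one clear rule for testing. But that rule rests on a classification that the protocol's own definition of childbearing potential does not support, and it errs in the less cautious direction.

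Section 21.1 also lets the investigator set entry requirements for permanent infertility from other medical causes. That clause does not close the gap: it mandates no test, and Appendix B itself treats tubal occlusion as contraception.

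Three points on size deserve weight.

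- The 0.5% to 3% share has no source in the protocol, so the bound is conditional on it.
- A full year of failures is generous, because the test matters only for a pregnancy still unrecognised at admission. If that window is 4 to 8 weeks (also an assumption), the favipiravir-arm figures fall to about 0.0125 × 4/52 = 0.001 and 0.075 × 8/52 = 0.012. Only that arm bears on harm from the drug.
- This version is dated April 2021, enrolment began in May 2020, and the study was due to end in October 2021. An amendment would reach only women not yet enrolled, so the counts over all 500 overstate what can still be changed.

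The last objection is that amending Appendix B instead would also restore consistency. It would, but these women would remain untested.

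**Conclusion.** The inconsistency is real, and the protocol as written leaves premenopausal women with tubal ligation without a required pregnancy test. The textual point is certain. The safety consequence is very small: well under one expected pregnancy on favipiravir across the assumed range, even with the deliberately high full-year count. Nothing in the trial's validity or statistical analysis depends on it. This is an optional correction, worth making because it is cheap and concerns a potentially teratogenic drug.

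**What to change.** In the first route of criterion 4, in both the synopsis and Section 8.2, replace tubal ligation with bilateral salpingectomy. The list then matches Section 21.1 for premenopausal women, and a woman with tubal ligation moves to the second route and is tested. She still meets the contraception requirement, because Section 21.2 accepts bilateral tubal occlusion.

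The cost is one wording change in two places at the next amendment, plus one pregnancy test for each such woman still to be enrolled. Over the whole trial that would be about 3 to 15 tests under the assumed range, and fewer for the recruitment that remains.

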#### 8.3. Exclusion Criteria

The participant may not enter the study if ANY of the following apply:

- 1. Pregnant or breast feeding, due to potential teratogenicity
- 2. Hepatic impairment (AST or ALT > 3.5 x upper limit of normal)
- 3. Presently enrolled in an interventional drug study
- 4. Unable to take medication via the oral or nasogastric route
- 5. Known sensitivity Favipiravir

#### 8.4. Recruitment

Potential participants will be identified on admission to hospital by a member of the clinical or research team with either suspected or proven COVID-19 infection. Potential participants (or their acting representative) will be informed about the study and provided a copy of the patient information sheet (PIS) and the informed consent form (ICF), with sufficient time (according to clinical context) provided to consider the information before informed consent is sought.

All patients consented must be assessed as eligible by a clinician. Participation in this trial should be recorded in their patient notes and on the trial database.

Written informed consent must be obtained prior to any study specific procedures, unless participant consent has been given orally due to COVID-19 infection in accordance with local procedures as approved by the local ethics committee.

Sites must keep a record of all screening and enrolled participants using screening and enrolment logs. Subjects will be assigned a subject ID number at the time of randomisation. Once a subject number has been assigned to a subject, it will not be reassigned to any other subject.

#### 8.5. Consent

The informed consent procedure in PIONEER shall be compliant with the trial protocol and GCP, as well as with EU and national regulations.

Where written consent cannot be safely taken due to COVID-19 infection, participant consent can be given orally by the trial participant as per Article 2(j) of Directive 2001/20/EC, in the presence of an impartial witness. Whereby the witness will be required to sign and date the informed consent form and the investigator will provide documented clarification on how the impartial witness was selected.

Alternatively, the trial participant and the person obtaining consent may sign and date separate informed consent forms, which shall ultimately be stored together in the site file as per local policy.

## 8.6. Participant Withdrawal

Participants may withdraw from the study at any time at their own request, and for any reason or they may be withdrawn at any time at the discretion of the study team or Sponsors for safety, administrative or any other reasons. In any circumstance, every effort should be made to document subject outcome, if possible. The investigator should inquire about the reason for withdrawal. If the reason for removal of a

participant from the study is an AE or an abnormal laboratory test result, the principal specific event or test will be recorded on the CRF. Withdrawn participants may be replaced at the discretion of Chief Investigator. The lead sponsor may retain and continue to use any data collected before such withdrawal of consent unless the patient wishes all their data to be removed from the trial.

#### 8.7. Allocation of Intervention

Eligible participants will be randomised 1:1 to one of the two arms using a web-based randomisation portal using blocks of randomly varying length.

An immediate allocation of treatment intervention as well as a participant identification number will be provided by the system to the person entering the data.

#### 8.8. Duration of Involvement

The duration of study treatment is 10 days and participants will remain on the study for 28 days from randomisation.

#### 9. STUDY INTERVENTIONS

A study intervention is defined as any investigational intervention(s) administered to a study participant in accordance study protocol.

For the trial medicinal supplies will be packaged and affixed with a label in accordance with regulatory requirements.

## 9.1. Study Investigational Medicinal Product

Refer to appendix C for description of study drug.

Participants will be randomised 1:1 to receive:

- Favipiravir 1800mg BD for 1 day, with 800mg BD for 9 days thereafter.
- Standard of care

Favipiravir dosing will consist of 1800mg BD for one day given orally, followed by 800mg BD for 9 days. This was the dose regime that showed that showed a significant time to alleviation of influenza symptoms in a Japanese phase II study on influenza (NCT03394209) and the dose regime studied in the US phase III studies in subjects with influenza (NCT02008344). Favipiravir has demonstrated *in-vitro* activity against SAR-CoV-2 in Vero E6 cells (EC50 = 61.88  $\mu$ M, (9.7 g/ml) CC50 > 400  $\mu$ M, SI > 6.46). This is higher than what was found for influenza (1 - 25  $\mu$ M).(12)

Regime day	1	2	3	4	5	6	7	8	9	10
Favipiravir	1800	800	800	800	800	800	800	800	800	800
(Twice daily; mg)	1800	800	800	800	800	800	800	800	800	800

Figure 2 INVESTIGATIONAL MEDICINAL PRODUCT DOSING REGIME

#### 9.2. Nasogastric/ Nasojejunal Administration

Favipiravir tablets can be crushed and dispersed in water for administration in enteral tubes. Crushed tablets should be dispersed in 10-15ml of distilled water in a syringe and allowed to dissolve. Shake well before administration and then the tube should be flushed after administration with 10ml distilled water.

#### 9.3. Treatment Administration

The participants' hospital clinicians are responsible for the administration of the allocated treatment and are free to modify or stop study treatment if clinically necessitated, without the need for the patient to withdraw from the study. Study treatment medication will be subject to the standard local pharmacy reviews, which will guide modifications to both the study treatment (i.e. dose adjustment for renal impairment) and the use of concomitant medication (e.g. in the case of potential drug interactions).

## 9.4. Drug Monitoring

Full blood count, Liver function tests and Urea & Electrolytes should be performed before a participant is randomised, with routine testing repeated at the 5 to 10 day follow-up visit (or beforehand if clinically indicated). Blood monitoring should be performed more frequently in participants with renal or liver impairment with the necessary dose adjustments implemented as necessary.

Where patients are discharged beforehand, clinical blood monitoring should be repeated at the day 5-10 and day 14-28 visits. This will allow optimal clinical monitoring of the patients through the study given the opportunities available. Inpatients will be receiving repeat testing as clinically indicated and this should be as per local policy given the preceding paragraph.

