## 9.6. Potential Risks

The following are known side-effects of the investigational medical product:

Favipiravir	
Common	Raised uric acid level (4.8%); diarrhoea (2.3%); reduced neutrophil count (1.8%); raised liver enzymes (1.6%); nausea (2.1%); urinary tract infection (1.5%), headache (1.1%), vomiting (1.0%), blood triglycerides increased (1.9%)
Uncommon or Rare	Confusion; fulminant hepatitis; renal failure; agranulocytosis; Steven- Johnson syndrome (toxic epidermal necrolysis)
Cautions	Participants on theophylline, pyrazinamide, repaglinide, or famiciclovir should be treated with caution due to drug interactions

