#### 10. PARTICIPANT ASSESSMENTS

#### 10.1. Baseline Data Collection

The following information will be collected:

- Demographics
- Co-morbidities
- Medication history and allergy
- Date of COVID-19 symptom onset
- Date of confirmatory COVID-19 test (SARS-CoV-2 infection by PCR or other National standard)
- Smoking status
- Travel history for preceding 6 months
- Clinical parameters (Heart rate, Respiratory rate, Oxygen Saturations)
- Baseline bloods (Full blood count, C-reactive protein, procalcitonin (if this is not part of site
  routine testing it is not required by protocol), ferritin, urea, d-dimer, LDH, troponin, urea &
  electrolytes, liver function (if available)

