#### Clinical

Nonclinical studies have shown mild phototoxicity. One study subject experienced mild photosensitivity (rash) following a tanning bed session. All subjects should avoid excessive exposure to sunlight or artificial ultraviolet light.

Clinical studies of subjects with renal impairment have shown higher exposure levels and reduced urinary excretion compared to subjects with normal renal function. No alternative dosing is recommended. No data are available in patients with end stage renal disease or renal failure.

Mild to moderate, asymptomatic elevations in serum uric acid have been observed in healthy volunteers and subjects with influenza treated with Favipiravir in clinical studies. The changes have been reversible upon Favipiravir discontinuation. Laboratory values and potential AEs related to increases in uric acid levels should be monitored.

In two proof-of-concept studies of orally administered Favipiravir against lethal Ebola virus infection in cynomolgus macaques, GI tract lesions were observed that were not consistent with the known natural history of Ebola nor with previous animal and clinical studies of Favipiravir. The contributing factors responsible for these lesions cannot be determined with certainty. However, evidence suggests that bacterial infections and pre-existing enterocolitis in the treated macaques may have been responsible for the confounding results, and an ongoing risk to patients may not exist.

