## **Drug Interaction**

A series of healthy volunteer studies have been completed to investigate possible favipiravir interactions with drugs that are either frequently administered to influenza patients or are eliminated by pathways common to favipiravir

- Acetaminophen: Favipiravir in combination with acetaminophen increased acetaminophen blood levels 14 to 17% based on plasma AUC comparisons.
- Hydralazine: Co-administration of favipiravir and hydralazine resulted in a 13% reduction in hydralazine AUC. No changes in favipiravir PK were observed.
- Ortho Novum® 1/35 (norethindrone and ethinyl estradiol): Favipiravir co-administration increased both norethindrone and ethinyl estradiol blood levels. Norethindrone plasma AUC increased 47% and ethinyl estradiol plasma AUC increased 43%. One subject discontinued the study due to transient, mildly elevated ALT (2.8 × normal) and AST (1.7 × normal).
- Oseltamivir: Favipiravir did not alter the PK of oseltamivir nor did oseltamivir alter favipiravir PK.
- Raloxifene: Co-administration of favipiravir with raloxifene, a potent aldehyde oxidase inhibitor, did not appreciably alter favipiravir PK. Favipiravir plasma AUC was reduced 15% when administered in combination with raloxifene.

- Repaglinide: Favipiravir administration with repaglinide, an anti-diabetic agent that is extensively
  metabolized by CYP2C8 and CYP3A4, increased repaglinide plasma AUC 30 to 50% due to
  inhibition of CYP2C8.
- Pyrazinamide: Pyrazinamide administration with favipiravir examined possible renal urate transporter interactions. Pyrazinamide increased blood uric acid levels 2 to 9 mg/dL over baseline. The addition of favipiravir increased blood uric acid levels 4 to 11 mg/dL over baseline, indicating a moderate additive effect. One subject developed headache and fever in association with elevated liver function tests (AST, ALT, gamma-glutamyl transferase, and lactate dehydrogenase) following pyrazinamide and favipiravir co-administration, which was determined to be an serious adverse event (SAE) and resolved upon discontinuation.

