#### **Adverse Reactions**

Data from three clinical studies in suspected or confirmed influenza treated on a 5 day regimen of favipiravir at the proposed dose (or a broadly similar exposure given TID).

The majority of all TEAEs in these studies have been mild in severity and assessed as unrelated to study drug and resolved without sequelae.

Table 1 Number of Subjects with TEAE by System Organ Class (SOC) and PT with at Least 0.5% Occurrence (US213b, US316, US317)

Safety Population	Pooled Placeb	o Pooled Favipiravir
SOC PT	(N = 894)	(N =1653)
	n (%)	n (%)
Number of Subjects With	227 (25.4)	419 (25.3)
Adverse Event(s)		
Gastrointestinal disorders	75 ( 8.4)	122 ( 7.4)
Diarrhoea	39 ( 4.4)	38 ( 2.3)
Nausea	16 ( 1.8)	34 ( 2.1)
Vomiting	8 ( 0.9)	16 ( 1.0)
Abdominal pain upper	5 ( 0.6)	8 ( 0.5)
Dyspepsia	5 ( 0.6)	6 ( 0.4)
Abdominal pain	7 ( 0.8)	4 ( 0.2)
Infections and infestations	59 ( 6.6)	82 ( 5.0)
Urinary tract infection	16 ( 1.8)	24 ( 1.5)
Sinusitis	6 ( 0.7)	6 ( 0.4)
Oral herpes	5 ( 0.6)	2 ( 0.1)
Pneumonia	5 ( 0.6)	2 ( 0.1)
	39 ( 4.4)	86 ( 5.2)
Investigations		
Blood triglycerides increased	11 ( 1.2)	32 ( 1.9)
Alanine aminotransferase increased	11 ( 1.2)	31 ( 1.9)
Aspartate aminotransferase increased	11 ( 1.2)	21 ( 1.3)
PIONEER Version 2.4 21 st April 20	021	CONFIDENTIAL Page 41

Blood cholesterol increased	6 ( 0.7)	5 ( 0.3)
	23 ( 2.6)	39 ( 2.4)
Nervous system disorders		
Headache	8 ( 0.9)	18 ( 1.1)
Dizziness	5 ( 0.6)	8 ( 0.5)
	48 ( 5.4)	55 ( 3.3)
Respiratory, thoracic and		
mediastinal disorders		
Bronchitis	11 ( 1.2)	6 ( 0.4)
Epistaxis	8 ( 0.9)	8 ( 0.5)
Vascular disorders	5 ( 0.6)	23 ( 1.4)
Dizziness	2 ( 0.2)	14 ( 0.8)

Note: AEs are classified according to SOC and PT of MedDRA Version 15.0. Subjects are counted once within each SOC or PT.

Note: US213b BID and TID, US316 and US317 are pooled for analysis. In US213b, TEAE if an AE started within 15 days of first dose. In US316 and US317, TEAE if an AE occurred within 22 days of first dose.

Table 2: Expected Adverse Drug Reactions by PT (US213b, US316, US317)

PT	Pooled Favipiravir N = 1653 n (%)	
Diarrhoea	38 (2.3)	
Nausea	34 (2.1)	
Blood triglycerides increased	32 (1.9)	
ALT increased	31 (1.9)	
Urinary tract infection	24 (1.5)	
AST increased	21 (1.3)	
Headache	18 (1.1)	
Vomiting	16 (1.0)	

Note: AEs are classified according to PT of MedDRA Version 15.0. Subjects are counted once within PT.

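### The protocol asks for uric acid to be monitored and lists its rise as the most frequent side effect, but the blood tests fixed in Sections 9.4 and 10.1 leave it out

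*Protocol*

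**What the plan says.** Four places in the protocol bear on this.

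- **Appendix C, Section 22.1, Clinical precautions.** It reports uric acid rises in healthy volunteers and influenza patients given favipiravir. It describes them as mild to moderate, asymptomatic and reversible when the drug is stopped, and concludes: "Laboratory values and potential AEs related to increases in uric acid levels should be monitored". Section 9.1 refers the reader to this appendix for the study drug.
- **Section 9.6, Potential Risks.** Raised uric acid stands first among the common side effects, at 4.8%.
- **Section 9.4, Drug Monitoring.** "Full blood count, Liver function tests and Urea & Electrolytes should be performed before a participant is randomised", and then "with routine testing repeated at the 5 to 10 day follow-up visit (or beforehand if clinically indicated". Participants discharged early should have clinical bloods at the day 5 to 10 and day 14 to 28 visits. Inpatients are otherwise tested as clinically indicated under local policy.
- **Section 10.1, Baseline Data Collection.** Besides full blood count, C-reactive protein, procalcitonin, urea and electrolytes and liver function, the list has "ferritin, urea, d-dimer, LDH, troponin". Uric acid is not on it.

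**The concern.** The protocol states a precaution in one place and fixes the blood tests in another, and the two do not meet. Site staff work from Sections 9.4 and 10.1. Someone who follows those lists exactly has no prompt to request uric acid.

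The gap matters because of the kind of effect. The appendix calls the rise asymptomatic, so it will seldom give a clinical reason for a test. The telephone interview in Section 10.3, for participants discharged before day 10, asks about adverse events and general health and cannot detect it either. Section 12.2 counts abnormal laboratory findings not related to COVID-19 as adverse events, but a result can be abnormal only if the assay is run. At stake is the completeness of the safety record for the side effect that the protocol itself ranks as most frequent.

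**Working it through.** This is mainly a comparison of texts, with a little arithmetic for scale.

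**Step 1: is uric acid the most frequent listed side effect?** The Section 9.6 rates in descending order are 4.8% (uric acid), 2.3% (diarrhoea), 2.1% (nausea), 1.9% (triglycerides), 1.8% (neutrophil count), 1.6% (liver enzymes), 1.5% (urinary tract infection), 1.1% (headache) and 1.0% (vomiting). Uric acid is highest, at 4.8 / 2.3 = 2.1 times the next rate.

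**Step 2: is it measured under the schedule?**

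| Section | What is fixed | Uric acid named? |
|---|---|---|
| 9.4, before randomisation | Full blood count, liver function, urea and electrolytes | No |
| 9.4, day 5 to 10 | Routine testing repeated, no analyte added | No |
| 9.4, day 14 to 28 (if discharged beforehand) | Clinical blood monitoring repeated | No |
| 10.1, baseline | Full blood count, C-reactive protein, procalcitonin, ferritin, urea, d-dimer, LDH, troponin, urea and electrolytes, liver function | No |
| 10.2, inpatient | Whatever routine results exist | No |

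Urea is a different analyte from uric acid, and a urea and electrolytes panel does not by convention include urate. A local laboratory may add it, but nothing in the protocol requires this. No other section schedules it.

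**Step 3: how many participants might be affected?** Inputs: 250 per arm (Section 13.2) and 4.8% (Section 9.6). Expected number = 250 × 0.048 = 12. The 2.5th and 97.5th percentiles of Binomial(250, 0.048) are 6 and 19. This carries the Section 9.6 rate over to patients hospitalised with COVID-19. The protocol gives no source for the rate and does not say that it applies to them, so the figure shows scale only and is not a prediction.

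**Step 4: how many assays would a fix need?** With 500 participants and two time points (before randomisation and day 5 to 10), 500 × 2 = 1,000 at most. If every participant also had a day 14 to 28 test, the ceiling would be 500 × 3 = 1,500. Since enrolment began in May 2020, an amendment that covers only participants still to be recruited would need fewer.

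**The case against.** The best case for leaving the text alone runs as follows. Appendix C is part of the protocol, so a site that ignores uric acid is already departing from it. The appendix passage is general product information with no schedule, threshold or action, and it defers to the Investigator Brochure, which is not at hand. Section 9.4 allows earlier testing on clinical indication, and Section 10.2 collects routine results. By the protocol's own account the effect is mild to moderate and goes away, and measuring it would change no specified management.

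Much of this stands and limits the size of the point. It is wrong to say that a site can comply with the whole protocol and never measure uric acid; the accurate statement is that a site following Sections 9.4 and 10.1 would not be led to measure it. The rest does not close the gap. Testing on indication is a weak safeguard for a change without symptoms, and a precaution with no schedule needs the schedule to supply one.

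A reader might infer more from the same pages. Four such inferences are not supported:

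- **That the 4.8% is contradicted by Appendix C.** The table titled "Number of Subjects with TEAE by System Organ Class (SOC) and PT with at Least 0.5% Occurrence" shows no uric acid row, which might suggest a rate below 0.5%. But it shows no row for reduced neutrophil count either, which Section 9.6 puts at 1.8%. Section 9.6 evidently draws on another source. The table also counts reported adverse events, and symptomless laboratory rises may not have been reported as such.
- **That the pyrazinamide result argues for testing everyone.** The finding "The addition of favipiravir increased blood uric acid levels 4 to 11 mg/dL over baseline, indicating a moderate additive effect" comes from a healthy-volunteer study of combined use. Section 9.6 already names pyrazinamide as a caution, and Section 9.3 puts concomitant drugs under pharmacy review.
- **That discretionary testing would be more frequent in the favipiravir arm.** This is possible in an open-label trial, but nothing in the protocol shows it, and no listed endpoint compares uric acid.
- **That the 10-day course makes this worse.** The Appendix C safety data are from patients "treated on a 5 day regimen of favipiravir at the proposed dose", and Section 5 also gives the 5-day duration. Section 9.1 describes the earlier regimen loosely, but that is a matter of wording and does not bear on whether uric acid is scheduled.

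**Conclusion.** The mismatch is real and can be read directly from the protocol: a monitoring precaution for its most frequent listed side effect is not carried into the blood tests that it fixes. The severity is minor. The effect is described as mild to moderate, asymptomatic and reversible, and the primary efficacy analysis does not depend on it.

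The textual finding needs no assumption beyond the usual content of a urea and electrolytes panel. The size, about 12 of 250, rests wholly on the assumption that 4.8% applies to this population. The change is worth making because it is cheap and makes the protocol consistent with itself. The documents do not show that participants are at serious risk without it.

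**What to change.** - **Section 9.4:** add serum uric acid to the bloods before randomisation and at day 5 to 10, in both arms. Where day 14 to 28 clinical bloods are already taken, include it there so that reversal after treatment can be checked.
- **Section 10.1:** add it to the baseline list so that the two sections agree.

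The dose, treatment duration, sampling windows and visits stay as they are. The cost is the assays counted above, one eCRF field, a protocol amendment and some additional records of mild adverse events. No new visit is needed. The assay is meant to run on clinical samples already scheduled; the protocol does not give their volume or tube type, so sites should confirm that these are suitable.
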